2.1.2 Exclusion Criteria

- Patients who have had standard-of-care anti-cancer therapy within 2 weeks of treatment initiation or therapy with investigational agents (e.g. chemotherapy, immunotherapy, endocrine therapy, targeted therapy, biologic therapy, tumor embolization, monoclonal antibodies or other investigation agents), large field radiotherapy, or major surgery within 4 weeks of treatment initiation.
- Any unresolved toxicity NCI CTCAE v.5 Grade ≥ 2 from previous anticancer therapy with the exception of alopecia, vitiligo, and the laboratory values defined in the inclusion criteria. Patients with Grade ≥ 2 neuropathy will be evaluated on a case-by-case basis.
- Has biliary duct obstruction, unless a treatable, clinically relevant obstruction has been relieved by internal endoscopic drainage/stenting, palliative by-pass surgery or percutaneous drainage prior to treatment initiation.
- Patients with known brain metastases are excluded from this clinical trial because of their poor prognosis and because they often develop progressive neurologic dysfunction that would confound the evaluation of neurologic and other adverse events.
- Patients with signs of liver failure, e.g. clinically significant ascites, encephalopathy, or variceal bleeding within six months before treatment initiation.
- History or current evidence of retinal vein occlusion (RVO) or current risk factors for RVO (e.g. uncontrolled glaucoma or ocular hypertension, history of hyper viscosity or hypercoagulability syndromes)
- Current evidence of uncontrolled, significant intercurrent illness including, but not limited to, the following conditions:
 - Cardiovascular disorders: Congestive heart failure New York Heart Association class 3 or 4, unstable angina pectoris, serious cardiac arrhythmias, stroke (including transient ischemic attack [TIA]), myocardial infarction (MI), or other ischemic event, or thromboembolic event (e.g., deep venous thrombosis, pulmonary embolism) within 3 months before treatment initiation
 - History of glucose-6-phosphate dehydrogenase (G6PD) deficiency
 - History of seizures
 - Patients who are planning on embarking on a new strenuous exercise regimen after first dose of study treatment. Muscular activities, such as strenuous exercise, that can result in significant increases in plasma creatine kinase (CK) levels should be avoided while on study treatment

- Patients who have neuromuscular disorders that are associated with elevated CK (e.g., inflammatory myopathies, muscular dystrophy, amyotrophic lateral sclerosis, spinal muscular atrophy)
- Impairment of gastrointestinal function or gastrointestinal disease (e.g., ulcerative disease, uncontrolled nausea, vomiting, diarrhea, malabsorption syndrome, or small bowel resection that under the judgment of the principal investigator (PI) may impair absorption of study drugs)
- Any other condition that would, in the Investigator's judgment, contraindicate the patient's participation in the clinical study due to safety concerns or compliance with clinical study procedures, e.g., infection/inflammation, intestinal obstruction, unable to swallow medication (patients may not receive drug through a feeding tube), social/psychological issues, etc.
- Screening corrected QT interval by Fridericia's (QTcF) > 500 msec
- Known infection with human immunodeficiency virus (HIV), unless patient is on effective anti-retroviral therapy with undetectable viral load within 6 months of treatment initiation
- Known chronic hepatitis B virus, unless hepatitis B virus (HBV) viral load is undetectable.
- Known history of hepatitis C virus (HCV) infection, unless completed treatment and cured with undetectable HCV viral load.
- Known prior severe hypersensitivity to study drugs or any component in its formulations (CTCAE v5.0 grade ≥ 3).
- Pregnant women are excluded from this study because study therapy can cause fetal harm. Because there is potential risk for adverse events in nursing infants secondary to treatment of the mother with study therapy, breastfeeding should be discontinued if the mother is treated with study drugs.

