2.2.2 Screening activities performed after a consent for screening has been signed

The following activities will be performed only after the subject has signed the study consent OR the consent for study 01-C-0129 (provided the procedure is permitted on that study) on which screening activities may also be performed. Assessments performed at outside facilities or on another NIH protocol within the timeframes below may also be used to determine eligibility once a patient has signed the consent.

The following must be completed within 28 days prior to initiation of study treatment unless otherwise noted below:

- Complete Medical History and Physical Evaluation (including height, weight, vital signs, and ECOG performance status).
- EKG
- Echocardiogram
- Cardiology Consultation (if clinically indicated)
- Ophthalmological evaluation
- CT scan of chest, abdomen and pelvis (or MRI of chest, abdomen and pelvis if clinically indicated)
- MRI of brain (if clinically indicated)
- Laboratory Evaluation
 - Hematological Profile: CBC with differential and platelet count.
 - Biochemical Profile: electrolytes, BUN, creatinine, AST, ALT, total and direct bilirubin, calcium, phosphorus, albumin, magnesium.
 - 24-hour urine collection (if clinically indicated)
 - Serum or urine pregnancy test for female participants of childbearing potential (within 2 weeks of enrollment).
 - HIV, Hepatitis B and C serology and/or viral load (if clinically indicated)
 - TB testing (if clinically indicated)
 - Troponin I (if clinically indicated)
- Documentation of histologic confirmation of BTC or carcinoma highly suggestive of a diagnosis of BTC (at any time point prior to enrollment). If there is no available documentation, biopsy will be performed to confirm the diagnosis.
- KRAS mutation status will be confirmed by NCI Laboratory of Pathology with TruSight™ Oncology 500 panel (at any time point prior to enrollment). If there is no available tumor sample, biopsy will be performed to confirm KRAS mutational status. Note: if participant has documentation of KRAS mutation status performed with FDA approved test (see Study Instrument) from certified laboratory, confirmation with TruSight™ Oncology 500 panel can be omitted.

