⁶ EKG must be performed at screening and on Day 1 of every cycle. Echocardiogram must be completed at screening, C2D1, and every 3 cycles thereafter (i.e. C5D1, C8D1, etc.) and as clinically indicated. Troponin I test and cardiology consult only if clinically indicated.

⁷ HIV, Hepatitis B and C serology. If screening serology results indicate potential HBV or HCV infection, viral load will be tested before starting investigational agents. TB testing will be performed only if clinically indicated.

⁸ Biochemical Profile: electrolytes, BUN, creatinine, AST, ALT, total and direct bilirubin, calcium, phosphorus, albumin, magnesium.

⁹ Pregnancy test for female participants of childbearing potential (serum or urine; if urine is positive it must be confirmed with serum test

Abbreviated Title: Trametinib and HCQ in BTC

Version Date: 04/06/2022

¹⁰ CT scan of chest, abdomen and pelvis (or MRI of chest, abdomen and pelvis if clinically indicated) every 8 (+/-1) weeks after start of study therapy. If patient taken off treatment for reason other than progression, CT scans will continue until progression or 5 months have passed since the start of study therapy whatever comes earlier. MRI of brain can be done at screening if clinically indicated.

¹¹ Mandatory tumor biopsies will be performed at baseline and any day during week 3 of cycle 2. If patient disease progresses before this, post-treatment biopsy might be performed per PI discretion at the time of progression.

¹² On Day 1 of cycles 1-4, then every 12 weeks until PD

¹³ +/- 1 week

¹⁴ After Safety Follow Up visit, subjects will be followed for adverse events by phone call or e-mail at 60 (+/- 14 days) and 90 (+/- 14 days) days. After that every 6 (\pm 1) months by phone call or e-mail for survival. If patient is taken off treatment for reason other than disease progression before 5 months have passed since the start of study therapy, we will continue to invite patient every 8 (+/-1) weeks for imaging studies until disease progression or 5 months have passed since the start of study therapy whatever comes earlier. Outside scans are acceptable.

¹⁵ If patients are not willing to come to the NIH Clinical Center, they may be followed by phone call or e-mail.

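### The plan requires a screening echocardiogram but sets no LVEF limit for entry, although the trametinib experience it cites excluded abnormal LVEF

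*Combined protocol and SAP*

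**What the plan says.** **Screening.** The list in Section 2.2.2 opens with "The following must be completed within 28 days prior to initiation of study treatment unless otherwise noted below" and includes an EKG and an echocardiogram without qualification. Cardiology consultation and troponin I are listed only for clinical need. Study Calendar footnote 6 (Section 3.4) repeats this: "Echocardiogram must be completed at screening, C2D1, and every 3 cycles thereafter", with further echocardiograms as clinically indicated, and "Troponin I test and cardiology consult only if clinically indicated".

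**Entry criteria.** The organ-function table in 2.1.1 covers marrow, liver and kidney and has no cardiac row. In 2.1.2 the cardiac exclusion reads "Cardiovascular disorders: Congestive heart failure New York Heart Association class 3 or 4, unstable angina pectoris" and goes on to list clinical events. It sits under a general heading, "significant intercurrent illness including, but not limited to, the following conditions". A separate clause lets the investigator refuse anyone with a condition judged to contraindicate "participation in the clinical study due to safety concerns". The only numeric cardiac limit is on the EKG: QTcF above 500 msec. Another exclusion covers unresolved toxicity of Grade 2 or worse from previous anticancer therapy. No LVEF value appears in either list.

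**Cited experience.** Section 1.2.5.3 reports that abnormal LVEF, acute coronary syndrome within 6 months and NYHA class II or greater heart failure were excluded.

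**On treatment.** Table 6 (Section 3.3.3) withholds trametinib for an asymptomatic absolute LVEF fall of 10% or more that ends below the LLN. Trametinib resumes at a lower dose if LVEF returns to normal and is otherwise stopped for good. It is also stopped for symptomatic cardiomyopathy, or for a fall of more than 20% that ends below the LLN.

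**The concern.** A mandatory pre-treatment test whose result decides nothing under the written criteria leaves the decision to whoever reads it. Here the test is the one that would show the condition most relevant to both drugs. Section 1.2.5.2 describes cardiomyopathy with trametinib, and Section 1.2.6.2 describes life-threatening and fatal cardiomyopathy with HCQ. Entry is also looser than in the cited trametinib experience on two measures, LVEF and heart-failure class, and the protocol gives no reason.

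Two things are at stake. The first is patient safety: a patient with a low starting LVEF could be exposed on one investigator's judgment and refused on another's, and the background cardiac rates used to weigh the risk come from patients selected differently. The second is operational: the Table 6 resume rule presumes a normal starting value. Neither touches sample size, error rates or the primary endpoint.

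**Working it through.** The plan states no figure on this point to reproduce. The check sets the sections side by side, with small arithmetic on the background rates.

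**1. Is there any LVEF limit at entry?** Sections 2.1.1 and 2.1.2 contain none. LVEF thresholds appear only as background in 1.2.5.2 and as on-treatment rules in Table 6.

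**2. What could keep out a patient with asymptomatic LVEF below the LLN?**
- The intercurrent-illness heading is open-ended, but it speaks of illness that is uncontrolled and significant. An asymptomatic low LVEF need not be either.
- The NYHA class 3 or 4 item does not reach a patient without symptoms.
- The unresolved-toxicity exclusion reaches only toxicity of earlier anticancer therapy.
- The safety-concerns clause does reach this patient, but by judgment and without a value.

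So the patient may enter unless judgment, or a link to earlier therapy, intervenes.

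**3. Do the quoted cardiac rates apply to this patient?** Inputs are from 1.2.5.2 and 1.2.5.3.
- METRIC: 14/211 = 6.6%, which agrees with the stated 7%.
- Pooled: 11% of N = 329, where 118 + 211 = 329.
- The exclusion of abnormal LVEF follows a description of both the pooled set and METRIC. It therefore covers at least part of the population behind these rates.
- The closest combination data (BAMM, Section 1.2.6.3, with dabrafenib added) show one Grade 3 ejection fraction decrease, 4%. Its LVEF entry rule is not given.

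None of these rates describes patients who start below the LLN.

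**4. When is the first scheduled check after exposure?** It is C2D1, after a 28-day cycle. In METRIC 5 of 14 cases were identified in the first month, which is 5/211 = 2.4% of treated patients. Median onset was 63 days and the earliest was day 16. The C2D1 timing follows the one-month check recommended in 1.2.5.2 and is not itself at fault. Screening is simply the only check before dosing.

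**5. Does Table 6 fit such a patient?** Let B be baseline LVEF, L the LLN and E the current value. The asymptomatic hold applies when E is at least 10 points below B and E < L. The resume rule needs a normal value, E ≥ L.
- If B ≥ L, full recovery gives E = B ≥ L, and trametinib resumes at a lower dose.
- If B < L, any 10-point fall already satisfies E < L. Full recovery gives E = B < L, and trametinib stops permanently.

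The rule works as intended only when B ≥ L. Section 3.1 allows HCQ to continue at the investigator's discretion.

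**The case against.** The strongest reply is that a required test without a cutoff is not an inconsistency. The guidance in 1.2.5.2 asks for LVEF before treatment, at one month and then every 2 to 3 months, and names no minimum for starting. The screening echocardiogram supplies the baseline that Table 6 needs. Other mandatory screening tests, such as visual acuity and visual field, also have no limit. This stands: the plan does not contradict itself. It does not answer why entry is wider than in the cited experience, or why the EKG has a stated limit and the echocardiogram does not.

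Second, safeguards exist: echocardiograms at C2D1, every 3 cycles and as clinically indicated; an EKG on Day 1 of every cycle; a cardiology consult if indicated; and the safety-concerns exclusion. A low value would be known before dosing. This also stands and lowers the stakes. But the monitoring acts after exposure, and the pre-dose routes name no LVEF value.

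Third, an LLN cutoff would bar a patient marginally below it whom a cardiologist might clear, in a disease with no standard second-line option. That is a real cost. It falls on candidates outside the population that 1.2.5.3 describes.

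Three stronger readings are tempting, and the documents do not support them.
- *Table 6 endangers these patients.* A reader might infer this from the misfit. Stopping trametinib is the cautious outcome, so the misfit costs treatment, not safety.
- *About a third of cardiac harm comes before the first on-treatment check.* The 5-of-14 figure might suggest this. It is a share of cases, equal to 2.4% of treated patients, and an earlier echocardiogram is allowed when clinically indicated.
- *At most about one patient would be withheld.* A reader might take 11% − 5% = 6% for falls between 10 and 20 points and multiply by 17 to get 1.02. This is not a bound. The 6% may be low for patients starting below the LLN, the accrual ceiling is 30, and the product counts withholds, not harm from starting treatment.

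**Conclusion.** The point holds as a gap in the safety criteria for entry. The written criteria let a patient with asymptomatic LVEF below the LLN start trametinib and HCQ unless an investigator decides otherwise, and the 7% and 11% rates may not describe that patient's risk. The Table 6 misfit is secondary and operational.

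The size is small but cannot be quantified. The documents give no prevalence of below-LLN LVEF among candidates, so neither an expected count nor an upper bound can be claimed. That few patients would be affected is a judgment. Power, alpha and the primary endpoint are unaffected.

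The conclusion rests on reading the general clauses in 2.1.2 as permitting refusal of such a patient without requiring it. It also assumes that the exclusions in 1.2.5.3 apply at least to part of the population behind the quoted rates. It is a cheap improvement to patient safety.

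**What to change.** Add one exclusion to Section 2.1.2: *Screening LVEF by echocardiogram below the institutional lower limit of normal.* Leave Table 6 unchanged. With this line every patient starts at or above the LLN, so recovery to baseline is a normal value and the resume rule works as written.

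The change needs one line of amendment text and no new procedure, because the echocardiogram is already done at screening. The downside is that a few candidates become ineligible where the protocol itself sees no standard second-line option. If the sponsor prefers to keep such patients eligible, the protocol should say so and adapt the Table 6 resume rule to a below-LLN baseline.

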Post marketing cases of life-threatening and fatal cardiomyopathy have been reported with use of HCQ as well as with use of chloroquine. Patients may present with atrioventricular block, pulmonary hypertension, sick sinus syndrome or with cardiac complications. ECG findings may include atrioventricular, right or left bundle branch block. Signs or symptoms of cardiac compromise have appeared during acute and chronic treatment. Clinical monitoring for signs and symptoms of cardiomyopathy is advised, including use of appropriate diagnostic tools such as ECG to monitor patients for cardiomyopathy during HCQ therapy. Chronic toxicity should be considered when conduction disorders (bundle branch block/atrio-ventricular heart block) or biventricular hypertrophy are diagnosed. If cardiotoxicity is suspected, prompt discontinuation of HCQ may prevent life-threatening complications. HCQ prolongs the QT interval. Ventricular arrhythmias and torsade's de pointes have been reported in patients taking HCQ. Therefore, HCQ should not be administered with other drugs that have the potential to prolong the QT interval

Worsening of psoriasis and porphyria:

Use of HCQ in patients with psoriasis may precipitate a severe attack of psoriasis. When used in patients with porphyria the condition may be exacerbated. The preparation should not be used in these conditions unless in the judgment of the physician the benefit to the patient outweighs the possible hazard.

Proximal Myopathy and Neuropathy:

Skeletal muscle myopathy or neuropathy leading to progressive weakness and atrophy of proximal muscle groups, depressed tendon reflexes, and abnormal nerve conduction, have been reported. Muscle and nerve biopsies have been associated with curvilinear bodies and muscle fiber atrophy with vacuolar changes. Assess muscle strength and deep tendon reflexes periodically in patients on long-term therapy with HCQ.

Neuropsychiatric events, including suicidality:

Suicidal behavior has been rarely reported in patients treated with HCQ.

Hypoglycemia:

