1.2.6.3 Toxicities of the combination of trametinib and HCQ

There is no data available in terms of this combination though there should have this information accessible in the near future since several trials involved with this combination is ongoing. However, there is safety data from the BAMM trial (NCT02257424), that is designed for patients with advanced BRAF mutant melanoma treated with dabrafenib, trametinib, and hydroxychloroquine. The doses of trametinib and hydroxychloroquine used in the BAMM trial is the exact same as we plan in our trial except that we are not planning BRAF inhibitor dabrafenib. Therefore, this precious data will provide important reference for our trial. From personal communication with [name] (Primary Investigator of BAMM trial, University of Pennsylvania), we summarize the safety profile from BAMM trial as showed in the following **Table 3**.

Table 3. Safety profile in the BAMM Study

Adverse Event	Dabrafenib + trametinib + HCQ (BAMM)	
	Grade 1-2	Grade 3
Chills	14 (56%)	1 (4%)
Diarrhea	13 (52%)	0
Fever	13 (52%)	1 (4%)
Nausea	12 (48%)	1 (4%)
Fatigue	11 (44%)	0
Headache	9 (36%)	0
Myalgia	9 (36%)	0
Rash	9 (36%)	3 (12%)
Anorexia	8 (32%)	0
Dry mouth	7 (28%)	0
Pruritus	7 (28%)	0
Arthralgia	6 (24%)	0
Abdominal pain	5 (20%)	0
Vomiting	5 (20%)	0
Constipation	4 (16%)	0
Dysgeusia	4 (16%)	0
Creatinine increased	3 (12%)	0
Dehydration	3 (12%)	2 (8%)
QTc prolonged	3 (12%)	1 (4%)
Increased alanine aminotransferase	1 (4%)	2 (8%)
Ejection fraction decreased	0	1 (4%)

With the triplet combination, the most common adverse effects are chills, diarrhea, fever, nausea, rash, and fatigue with grade 1-2. No grade 4 AEs are reported. This information indicates the less adverse effects we foresee with trametinib and hydroxychloroquine in our trial.

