3.1.1 Dose Limiting Toxicity (DLT) (Safety Run-In only)

The DLT period is one cycle, 28 days, starting on Day 1 of cycle 1 after study drugs administration.

The following events will be considered DLTs (CTCAE v5.0) if attributable (definite, probable, possible) to the combination of study drugs:

Toxicity Category	DLT Criteria (grade per CTCAE 5.0)
Hematology	Grade ≥ 4 neutropenia lasting ≥ 7 consecutive days and/or not resolving within 48 hours to a grade 2 or less toxicity after correctible treatment
	Grade ≥ 4 thrombocytopenia lasting ≥ 7 consecutive days and/or not resolving within 48 hours to a grade 2 or less toxicity after correctible treatment
	Grade ≥ 3 neutropenia with fever (temperature ≥ 38.5 °C), not correctible within 48 hours to a grade 2 or less toxicity
Skin and subcutaneous tissue disorders	Grade ≥ 3 rash, hand-foot skin reaction or photosensitivity lasting > 7 consecutive days and/or not resolving within 48 hours to a grade 2 or less toxicity after correctible treatment
Eye disorders	Grade ≥ 2 retinal events lasting > 14 consecutive days confirmed by ophthalmologic examination
	Grade ≥ 3 retinal events confirmed by ophthalmologic examination, not correctible within 48 hours to a grade 2 or less toxicity
Gastrointestinal	Grade ≥ 3 nausea or vomiting lasting ≥ 7 days and/or not resolving within 48 hours to a grade 2 or less toxicity after correctible treatment
	Grade ≥ 3 diarrhea lasting ≥ 7 days and/or not resolving within 48 hours to a grade 2 or less toxicity after correctible treatment

	Grade \geq 3 total bilirubin not related to progression of disease, not correctible within 48 hours to a grade 2 or less toxicity
	Grade \geq 3 AST or ALT (isolated increases in AST without concomitant increases in ALT will not be considered DLT because of the non-specific nature of AST), not correctible within 48 hours to a grade 2 or less toxicity.
Hepatic	Patients with liver metastases will require AST or ALT levels 10 x ULN (isolated increases in AST without concomitant increases in ALT will not be considered DLT because of the nonspecific nature of AST).
	Grade \geq 4 alkaline phosphatase lasting \geq 7 consecutive days and/or not resolving within 48 hours to a grade 2 or less toxicity after correctible treatment
ECG QT Interval	QTcF interval \geq 501 ms on at least two separate ECGs, not correctible within 48 hours to a grade 2 or less toxicity

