3.3 Dose Modifications/Delay

In case of unbearable toxicity definitely attributed to one of the study drugs, patient will be taken off this drug and per PI discretion may continue treatment with the other drug only.

When, at the beginning of a treatment cycle, treatment delay related to one of the drugs is indicated, both study drugs should be held and resumed concurrently.

If, in the opinion of the investigator, a toxicity is considered to be due solely to one drug, the dose of the other drug may not require modification per PI discretion.

Dose interruptions for study treatment-related AEs are allowed as per the dose modification recommendations. Doses of any investigational product that were not administered due to toxicity will not be replaced within the same cycle. In addition to dose interruption, the need for a dose reduction at the time of treatment resumption should also be considered based on the dose modifications recommendations. If a toxicity-related dose delay of HCQ and trametinib for >28 days is required, treatment will be discontinued permanently, and the patient should be removed from study treatment.

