3.3.2 Hydroxychloroquine

Table 4 Guidelines for hydroxychloroquine-related toxicities

Adverse Event	1 st Occurrence	2 nd Occurrence
Hematology Grade 4 neutropenia lasting \geq 7 consecutive days Grade 4 thrombocytopenia \geq 7 consecutive days Grade \geq 3 neutropenia with fever (temperature \geq 38.5 °C)	Hold HCQ and trametinib. Continue weekly hematologic monitoring. Once AE resolves to \leq Grade 1, restart study drugs, with HCQ at next lower dose level.	Discontinue HCQ and trametinib
Skin and subcutaneous tissue disorders Grade \geq 3 rash, hand-foot skin reaction or photosensitivity lasting $>$ 7 consecutive days despite skin toxicity treatment	See Table 5	Discontinue HCQ and trametinib
Eye disorders Grade 2 retinal events lasting $>$ 14 consecutive days confirmed by ophthalmologic examination Grade \geq 3 retinal events confirmed by ophthalmologic examination	Hold HCQ and trametinib. Monitor until AE resolves to Grade \leq 1. Patients should be referred for ophthalmologic exam. Restart study drugs, with HCQ at next lower dose level.	Discontinue HCQ and trametinib
Gastrointestinal Grade \geq 3 nausea or vomiting lasting \geq 7 days despite optimal anti-emetic therapy	Hold HCQ and trametinib. Monitor until AE resolves to Grade \leq 1. Restart study drugs, with HCQ at next lower dose level.	Discontinue HCQ and trametinib
Grade \geq 3 diarrhea lasting \geq 7 days despite optimal anti-diarrhea treatment	See Table 6	Discontinue HCQ and trametinib
Hepato-biliary Grade \geq 3 total bilirubin felt to be not related to progression of disease Grade \geq 3 ALT (isolated increases in AST without concomitant increases in ALT will not be considered dose-limiting because of the non-specific nature of AST) Grade 4 alkaline phosphatase lasting \geq 7 consecutive days felt to be not related to progression of disease	Hold HCQ and trametinib. Monitor with weekly CMP until AE resolves to Grade \leq 1. Restart study drugs, with HCQ at next lower dose level.	Discontinue HCQ and trametinib
ECG QT Interval	Hold HCQ and trametinib. Monitor	Discontinue HCQ

Abbreviated Title: Trametinib and HCQ in BTC**Version Date: 04/06/2022**

Adverse Event	1 st Occurrence	2 nd Occurrence
QTcF interval \geq 501 ms on at least two separate ECGs	with ECG until AE resolves to Grade \leq 1. Restart study drugs, with HCQ at next lower dose level.	and trametinib

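### The QTcF entry limit sits 1 ms below the level at which both drugs are held, and restart needs a better QTcF than entry did; a small safety gap that one changed threshold closes

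*Combined protocol and SAP*

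**What the plan says.** - **Entry.** Section 2.1.2 excludes "Screening corrected QT interval by Fridericia's (QTcF) > 500 msec". A value of exactly 500 ms is eligible.
- **Hold.** Table 4 in Section 3.3.2 holds HCQ and trametinib when QTcF is at or above "501 ms on at least two separate ECGs".
- **Restart.** Patients are monitored "with ECG until AE resolves to Grade" 1 or lower, and HCQ then resumes one dose level down. Return to baseline is not offered as an alternative. A second occurrence ends both drugs.
- **Time limit.** Section 3.3: "If a toxicity-related dose delay of HCQ and trametinib for >28 days is required, treatment will be discontinued permanently".
- **Grade ordering.** The run-in criterion in Section 3.1.1 is a QTcF at or above "501 ms on at least two separate ECGs, not correctible within 48 hours to a grade 2 or less toxicity".
- **Drug effect.** Section 1.2.6.2: "HCQ prolongs the QT interval".
- **QT data.** Section 1.2.6.3 reports the BAMM trial, which added dabrafenib. It says "The doses of trametinib and hydroxychloroquine used in the BAMM trial is the exact same as we plan in our trial". Table 3 lists QTc prolongation as 3 (12%) at Grade 1-2 and 1 (4%) at Grade 3.

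**The concern.** The three QTcF thresholds were set without regard to each other. The entry limit lets a patient start a QT-prolonging drug almost at the value where the protocol stops it. The restart rule then asks for a lower QTcF than the one accepted at entry.

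Two things are at stake. The first is safety, since Section 1.2.6.2 mentions ventricular arrhythmia and torsade de pointes with HCQ. The second is treatment continuity: a patient could lose the combination because of a QTcF that the protocol had judged acceptable.

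**Working it through.** **Step 1: thresholds from the documents.** The margin between the highest eligible value and the hold trigger is 501 − 500 = 1 ms. Section 3.1.1 pairs 501 ms with recovery to grade 2 or less. So 501 ms lies above Grade 2, and a value just under it is most naturally read as Grade 2. Grade 1 or less, the restart condition, therefore lies below a value near 500 ms. The gap in ms cannot be read from the documents, because Section 6.4 cites CTCAE v5.0 without printing the QTc bands.

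**Step 2: observed QT events.** Table 3 implies n = 14/0.56 = 25. QTc prolongation of any grade is 4/25 = 16% (exact 95% CI 4.5% to 36.1%); Grade 3 is 1/25 = 4% (0.1% to 20.4%). BAMM's entry limit is not given, so these are not rates for patients who enter with a long QTcF.

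**Step 3: illustration, all inputs assumed.** Population mean m = 420 ms (430 ms also tried in Step 4); between-patient SD sb = 20 or 30; within-patient SD sw = 8 or 12; drug effect d = 5, 10 or 15 ms; independent ECGs; one screening ECG.

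- True baseline b given an observed x: normal with mean m + w(x − m) and variance w·sw², where w = sb²/(sb² + sw²).
- Hold on one pair of ECGs: E{[1 − Φ((500.5 − b − d)/sw)]²}.
- Restart given hold, drug effect gone, Grade 1 limit L: E{hold·Φ((L + 0.5 − b)/sw)}/E{hold}. For four ECGs with one qualifying reading enough, replace Φ by 1 − (1 − Φ)⁴.

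For x = 500 the extremes are:

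- sb = 20, sw = 12, d = 5: w = 400/544 = 0.735, mean baseline 420 + 0.735 × 80 = 478.8 ms, hold 0.049.
- sb = 30, sw = 8, d = 15: w = 900/964 = 0.934, mean baseline 494.7 ms, hold 0.679.

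| Observed at screening | Hold | Restart, one ECG (L = 480) | Restart, four ECGs (L = 480) |
|---|---|---|---|
| 500 ms | 5% to 68% | 2% to 25% | 6% to 60% |
| 490 ms | 1.5% to 32% | 5% to 35% | 15% to 73% |
| 481 ms | 0.3% to 10% | 10% to 44% | 29% to 82% |
| 460 ms | at most 0.5% | not tabulated | not tabulated |

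From 500 ms, the one-ECG restart chance is 0.1% to 9% if L = 470 and 13% to 52% if L = 490.

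**Step 4: how many patients.** With t = √(sb² + sw²), the share screened at 481 to 500 ms is Φ((500.5 − m)/t) − Φ((480.5 − m)/t). This is 0.0024 to 0.0242 for m = 420 and 0.0090 to 0.0445 for m = 430. Times 30, that is 0.07 to 1.33 candidates.

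Integrating the hold probability over that band gives the share who enter there and are held: 0.00004 (m = 420, sb = 20, sw = 8, d = 5) to 0.0128 (m = 430, sb = 30, sw = 8, d = 15), or 0.004% to 1.3%. Times 17 this is 0.0007 to 0.22 patients; times 30, at most 0.38.

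The hold figures are for one pair of ECGs. Repeated visits would raise them somewhat.

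**The case against.** The strongest reply is that this is a preference. Admitting up to 500 ms and holding from 501 ms applies one cut-off consistently, and a stricter restart after an on-drug event is sensible. Other safeguards exist:

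- named QT-prolonging drugs are prohibited and others need caution (Section 4.1);
- cardiology consultation is available at screening if indicated (Section 2.2.2);
- uncontrolled serious arrhythmia and advanced heart failure are excluded (Section 2.1.2);
- an EKG is due on Day 1 of each cycle, and electrolytes, calcium and magnesium are checked repeatedly (Section 3.4);
- the investigator may exclude on safety grounds (Section 2.1.2).

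Most of this stands. The hold and restart rules are defensible, and the safeguards address modifiable risk. None of them, however, sets a numeric entry limit below 500 ms. The exclusion for unresolved Grade 2 or higher toxicity does not fill the gap either: it covers only toxicity "from previous anticancer therapy with the exception of alopecia, vitiligo, and the laboratory values defined in the inclusion criteria", so a long QTcF from another cause remains eligible.

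A reader might infer that a patient admitted at 500 ms will almost certainly be held and then removed. The documents do not support that. The hold needs two ECGs, a single screening value near 500 ms tends to overstate the true baseline, monitoring continues until resolution, and Sections 3.1 and 3.3 let one drug continue at the PI's discretion.

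Nor is the primary analysis compromised. The two-stage rule does not depend on QTcF, and Section 3.4 continues imaging to progression or 5 months in patients who stop treatment for other reasons.

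**Conclusion.** The gap is real but small. That the margin is 1 ms and that restart is stricter than entry follow from the protocol's own thresholds and grade ordering. Everything about frequency rests on assumed QTcF distributions and drug effects. On those assumptions, fewer than 0.25 of 17 patients (at most about 0.4 of 30) would enter at 481 to 500 ms and be held. The chance of resuming from an observed 500 ms is 2% to 25% on one ECG, or about 6% to 60% on four, with 480 ms taken as the Grade 1 limit. These ranges are too wide to carry the argument, so it rests on the thresholds. The change is worth making because it is cheap and protects the few patients concerned; the trial's decision rule does not need it.

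**What to change.** In Section 2.1.2, exclude a screening QTcF above the CTCAE v5.0 Grade 1 upper limit, the same grade that Table 4 requires for restart. The sponsor should confirm that limit; if it is 480 ms, the criterion reads QTcF > 480 msec. Leave the hold, DLT and restart rules as they are.

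The cost is an amendment to one number. The screening EKG is already required (Section 2.2.2), so no test is added. The downside is that about 0.1 to 1.3 of 30 candidates would not be entered, under the assumptions above.
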